## 5. SAFETY ANALYSIS

The safety cohort will encompass all patients who have received at least one dose of trial treatment. Safety and tolerability of the afatinib treatments will be described by tabulation of the CTCAE V4 grade. In particular, safety analysis will include assessment of the experience of adverse events (AE) and serious adverse events (SAE), the frequency of AEs, the numbers of patients experiencing specific number of adverse events and their distribution by CTCAE V4 grade. Further exploration on AEs, with respect to their grade will include the presentation of maximum severity of AEs for each patient as well as the distribution of worst degree of severity by patient.

Note: If the same adverse event is recorded more than once for a specific patient, it will be counted only once keeping the one with the higher grade.

For a closer investigation and for purposes of medical review, information on AEs will also be provided by patient. This information will consist of AE description and grade, date of AE onset and end date (if the event is resolved), its potential relation to treatment and his/ her specific outcome.

A summary table of all the narratives of patients with SAE will also be provided.

Furthermore, the baseline symptoms experienced by some of the patients, which are not counted as adverse events –unless their grade was increased or they appeared as new events at a later period of time- will be presented separately.

## 6. REPORTING CONVENTIONS

P-values $\geq 0.001$  will be reported with two significant digits (e.g. p=0.26, p=0.026, p=0.003); p-values less than 0.001 will be reported as “<0.001”. The mean, 95% confidence limits, quantiles, and any other statistics, will be reported to one decimal. Hazard ratios (HRs) and their 95% CI's will be reported to two decimals. Estimated parameters, not on the same scale as raw observations (e.g. regression coefficients) will be reported to 3 decimals.

## 7. TECHNICAL DETAILS

Data will be analyzed using the SAS software package (version 9.4). The use of R language will also be considered for the production of specific plots.

A second statistician, the **reviewing statistician** will independently reproduce all analysis and summary statistics. The **reviewing statistician** will have an overview of the entire analysis and will explicitly check the code producing tables and figures as well as any other pieces of code as desired.

## 8. LISTING OF TABLES AND FIGURES

Table 1 gives a tabulation of the following aspects unique to each table:

- Title
- Numbering
- Population
- Endpoint(s)

- Time Points or details of how to conglomerate multiple observations
- Covariates or Subgroups used to break down summary statistics
- Which summary statistics will be calculated

For figures the equivalent information is summarized in Table 2 and includes the following:

- Title
- Numbering
- Population
- Type of figure
- Endpoint(s), and which is used for horizontal and vertical co-ordinates
- Statistic(s) used in calculating co-ordinate values used in the figure
- Covariates used within the figure used to determine colours or symbols

**Table 1.** Listing of Tables

| Table title  | Number | Population      | Endpoint  | Time Points or how to conglomerate | Covariates or Subgroups | Summary Statistics             | Formal Analysis  | Notes                    |
|--|--------|-----------------|---|------------------------------------|-------------------------|--------------------------------|--|--------------------------|
| Section I: Patient Accrual & Baseline Characteristics |        |                 |   |                                    |                         |                                |  |                          |
| Accrual by center  | 1      | Efficacy cohort | Accrual   | NA                                 | center                  | n (%)                          | NA   | Sorted by descending "n" |
| Patient and tumor baseline characteristics                       | 2      | Efficacy cohort | Gender
Smoking history
ECOG Performance status (at enrolment)
TNM staging
Age (yrs at enrollment) | Baseline                           | -                       | n (%)                          | NA   |                          |
| Information on previous and subsequent lines of treatment        | 3      | Efficacy cohort | Type of prior platinum treatment
Afatinib Treatment Line
Further treatment
Type of further treatment | Baseline, Follow-up                | -                       | n (%)                          | NA   |                          |
| History of previous diseases/conditions                          | 4      | Efficacy cohort | Types of previous diseases and conditions   | Baseline                           | -                       | n (%)                          | NA   |                          |
| Results of HER2 central testing                                  | 5      | Efficacy cohort | HER2 (ERBB2) mutation   | Baseline                           | -                       | n (%)                          | NA   |                          |
| Section II: Follow-up & Treatment Administration      |        |                 |   |                                    |                         |                                |  |                          |
| Time on follow-up and Time on treatment                          | 6      | Efficacy cohort | No. of patients still on f-up, no. of discontinuations  | End of follow-up                   | -                       | n (%)
median, interq. range | Reverse Censoring based on OS (f-up)
Kaplan – Meier analysis (both) |                          |
| Reasons of treatment failures                                    | 7      | Efficacy cohort | Reasons of treatment failures   |                                    |                         | n (%)                          | NA   |                          |
| Section III: Analysis of Primary Endpoint                 |        |                 |   |                                    |                         |                                |  |                          |

| Table title  | Number | Population                                  | Endpoint                   | Time Points or how to conglomerate   | Covariates or Subgroups | Summary Statistics   | Formal Analysis         | Notes |
|--|--------|---|----------------------------|--|-------------------------|--|-------------------------|-------|
| Disease Control Rate (DCR) at 12 weeks   | 8      | Interim evaluation cohort & Efficacy cohort | Disease Control (Yes / No) | 12-week evaluation (tumor assessment)  | -                       | n (%)  | NA                      |       |
| Section IV: Analysis of Secondary Efficacy Endpoints                              |        |   |                            |  |                         |  |                         |       |
| Best Overall Response and Objective Response Rate (ORR) for all enrolled patients (N=13) | 9      | Efficacy cohort                             | Best Overall Response, ORR | OR : The best overall response (CR or PR) across all assessment time-points according to RECIST Criteria 1.1, during the period from enrolment to termination of trial treatment. |                         | n (%)  |                         |       |
| Progression-free Survival (PFS) for all enrolled patients (N=13)                         | 10     | Efficacy cohort                             | PFS                        | PFS : time from the date of enrolment until documented progression or death without documented progression  | -                       | KM estimates: no. of patients, n(%) of PFS events, 12-week PFS (%) (95% CI), median PFS (in weeks) | Kaplan – Meier analysis |       |
| Overall Survival (OS) for all enrolled patients (N=13)                                   | 11     | Efficacy cohort                             | OS                         | OS : time from the date of enrolment until death  | -                       | KM estimates: no. of patients, n(%) of deaths, xx-weeks OS   | Kaplan – Meier analysis |       |

| Table title  | Number | Population      | Endpoint   | Time Points or how to conglomerate  | Covariates or Subgroups                      | Summary Statistics   | Formal Analysis         | Notes |
|--|--------|-----------------|--|---|--|--|-------------------------|-------|
|  |        |                 |  | from any cause  |  | (%) (95% CI), median OS (in weeks)   |                         |       |
| Section V: Translational Results                            |        |                 |  |   |  |  |                         |       |
| Translational results of central testing                           | 12     | Efficacy cohort | All biomarkers included in the central testing (wild-type, mutation detected, type of mutation detected) | Baseline  | -  | n (%)  |                         |       |
| Section VI: Exploratory Analysis of Efficacy Endpoints      |        |                 |  |   |  |  |                         |       |
| Primary endpoint by baseline characteristics                       | 13     | Efficacy cohort | DC at 12w achieved or not for each value of baseline characteristics                                     | 12-week assessment  | Different values of baseline characteristics | n (%)  | Fisher's exact test     |       |
| Primary endpoint by prior treatment                                | 14     | Efficacy cohort | DC at 12w achieved or not for each value of prior treatment  | 12-week assessment  | Different types of prior treatment           | n (%)  | Fisher's exact test     |       |
| Primary endpoint by translational results                          | 15     | Efficacy cohort | DC at 12w achieved or not for each value of biomarkers centrally tested                                  | 12-week assessment  | Different status of biomarkers tested        | n (%)  | Fisher's exact test     |       |
| Progression-free survival (PFS) for selected subgroups of patients | 16     | Efficacy cohort | PFS  | PFS: time from the date of enrolment until documented progression or death without documented progression | ERBB2, gender, smoking status                | KM estimates: no. of patients, n(%) of PFS events, 12-week PFS (%) (95% CI), median PFS (in weekw) | Kaplan – Meier analysis |       |
| Overall survival (OS) for selected subgroups of patients           | 17     | Efficacy cohort | OS   | OS: time from the date of enrolment until death from any cause  | ERBB2, gender, smoking status                | KM estimates: no. of patients, n(%) of deaths, xx-weeks OS (%) (95% CI), median OS (in weeks)      | Kaplan – Meier analysis |       |

| Table title   | Number | Population    | Endpoint | Time Points or how to conglomerate                                  | Covariates or Subgroups              | Summary Statistics                                  | Formal Analysis | Notes  |
|---|--------|---------------|----------|---|--------------------------------------|---|-----------------|--|
| Section VII: Safety Analysis                                       |        |               |          |   |                                      |   |                 |  |
| (Serious) Adverse event overview  | 18     | Safety cohort | AE / SAE | At the end of each treatment visit, Within 24h of occurrence of SAE | -                                    | n (%) of persons who have experienced >=1 AE or SAE | -               |  |
| Number of patients experiencing specific number of adverse events         | 19     | Safety cohort | AE       | At the end of each treatment visit                                  | -                                    | n (%)   | -               |  |
| Number of patients experiencing specific number of serious adverse events | 20     | Safety cohort | SAE      | At the end of each treatment visit, Within 24h of occurrence of SAE | -                                    | n (%)   | -               |  |
| Maximum severity of adverse events (AE/SAE) per patient                   | 21     | Safety cohort | AE / SAE | At the end of each treatment visit, Within 24h of occurrence of SAE | -                                    | n (%)   |                 |  |
| Distribution of adverse events (AE/SAE) by Grade                          | 22     | Safety cohort | AE / SAE | At the end of each treatment visit, Within 24h of occurrence of SAE | Severity grade (NCI CTCAE version 4) | n (%)   | -               | In case of multiple reports of the same AE/SAE (grouped according to CTCAE V4) for a particular patient, the |

| Table title                          | Number | Population    | Endpoint | Time Points or how to conglomerate                                  | Covariates or Subgroups | Summary Statistics | Formal Analysis | Notes                              |
|--------------------------------------|--------|---------------|----------|---|-------------------------|--------------------|-----------------|------------------------------------|
|                                      |        |               |          |   |                         |                    |                 | event is counted once.             |
| Baseline symptoms by patient         | 23     | Safety cohort | AE       | At baseline   | -                       | -                  | -               | Patients ordered by enrolment date |
| Adverse event information by patient | 24     | Safety cohort | AE / SAE | At the end of each treatment visit, Within 24h of occurrence of SAE | -                       | -                  | -               | Patients ordered by enrolment date |
| Narratives of patients with SAE      | 25     | Safety cohort | SAE      | At the end of each treatment visit, Within 24h of occurrence of SAE | -                       | -                  | -               | Patients ordered by enrolment date |

**Table 2.** Listing of Figures

| Title  | Number | Population   | Type of graph | Horizontal Variables            | Vertical Variables  | Groupings | Notes   |
|--|--------|--|---------------|---------------------------------|---|-----------|---|
| Section I: Patient Accrual & Baseline Characteristics   |        |  |               |                                 |   |           |   |
| Expected vs Observed Accrual   | 1      | Efficacy cohort  | Line graph    | time                            | cumulative number of patients                                 | -         | -   |
| Section II: Follow-up & Treatment Administration  |        |  |               |                                 |   |           |   |
| Kaplan Meir plot for Time-to-Treatment Failure (TTF)   | 2      | Efficacy cohort  | KM            | time                            | probability   | -         | -   |
| Section IV: Analysis of Secondary Efficacy Endpoints  |        |  |               |                                 |   |           |   |
| Plot of tumor response   | 3      | patients in efficacy cohort evaluable for tumor-response | Spider plot   | time                            | % change (in sum of diameter of target lesions) from baseline |           | It depends on the data whether it will be feasible to produce it  |
| Plot of duration of tumor response   | 4      | patients in efficacy cohort evaluable for tumor-response | Swimmer plot  | Duration of response (in weeks) | Patient id  | -         | It depends on the data whether it will be feasible to produce it  |
| Kaplan Meir plot for Progression Free Survival (PFS)   | 5      | Efficacy cohort  | KM            | time                            | probability   | -         | -   |
| Plot of Progression-free Survival by patient, according to primary endpoint (disease achieved at 12 weeks) | 6      | Efficacy cohort  | Bar-plot      | Patient id                      | PFS (in weeks)  | -         | Additional patients' characteristics will be shown below the bars |
| Kaplan Meir plot for Overall Survival (OS)   | 7      | Efficacy cohort  | KM            | time                            | probability   | -         | -   |

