Total trial duration: 40 months from enrolment of the first patient, including 6 months of follow-up from enrolment of the last patient.

2. Trial schedule

(refer to section 15 for details)

	Screening and eligibility within 28 days prior to enrolment	Afatinib treatment visits ¹³	End of treatment visit (within 30 days after treat. stop)	Follow-up before progression ¹⁴	Follow-up after progression ¹⁴
Written informed consent ¹	X				
Medical history	X				
Physical exam ² , PS, weight	X	X	X ³		
Local HER2-testing ¹⁵	X				
Haematology (WBC, haemoglobin, platelets, neutrophils)	X ⁴	X	X		
Chemistry: Na, K, calcium, albumin, magnesium	X ⁴	X ⁵	X		
Renal function: serum creatinine, calculated creatinine clearance	X	X	X		
Hepatic function: ALT, AST, bilirubin, GGT	X	X	X		
Electrocardiogram	X				
Pregnancy test if applicable ⁶	X		X		
CT thorax and upper abdomen ⁷	X	X	X ⁸	X ⁹	
Brain MRI or CT	X				
FFPE block (or 5-10 slides) from (primary or metastatic) biopsy for retrospective central HER2-testing	X ¹⁰				
Adverse events ¹¹	X	X ¹²	X	X	X
Record concomitant medication ¹¹		X	X	X	X
Afatinib 40mg p.o. daily until PD		X ¹²			
Survival status					X

- 1 – Any time before any trial-specific intervention
- 2 – Physical exam according to local standards, including blood pressure
- 3 – Blood pressure does not need to be reported at end of treatment visit.
- 4 – If haematology and/or chemistry were done more than 7 days prior to first dose, they need to be repeated before starting afatinib treatment.
- 5 – Will be repeated if clinically indicated according to local standards
- 6 – Women of childbearing potential (< 1 year without menstruation or < 2 years without menstruation following chemotherapy) must have a negative serum or urine pregnancy test before enrolment to the trial; the test has to be repeated within 7 days before starting afatinib treatment. Pregnancy tests should be repeated within 30 days after afatinib treatment stop. Any pregnancy occurring during treatment or within 6 months after treatment stop must be reported including its outcome.
- 7 – All patients must have a CT thorax and upper abdomen at baseline during screening, 6 and 12 weeks after first dose of trial treatment and then every 8 weeks (weeks 20, 28, 36 etc) until progression.
- 8 – CT to be repeated if not done within 6 weeks prior to end of treatment visit.
- 9 – In case of treatment stop for reason other than progressive disease, CT needs to be repeated every 8 weeks until progression.

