8.1. Screening

Note that written informed consent has to be obtained from the patient prior to any trial-specific intervention including any examination done specifically for screening purposes. The participating site should keep a screening log.

8.2. *HER2* mutation testing

The presence of *HER2* mutation needs to be confirmed according to the standard assay used in the local laboratory.

Appropriate molecular tests to detect clinically relevant *HER2* mutations should include direct sequencing of exon 20 of the *HER2* gene, validated PCR-based techniques, and clinically validated next generation sequencing methods, according to the standards of each laboratory. One block of FFPE material (or alternatively, 5-10 slides) from biopsy of primary tumor or metastatic lesion for each patient with *HER2* exon 20 mutation identified in the local laboratory will be subsequently sent for confirmation to the central laboratory at Medical University of Gdansk ([name], Dept. of Biology and Genetics, Collegium Biomedicaum, Medical University of Gdansk, Poland), see ***NICHE procedures manual*** for details. This biological material will be stored at the central laboratory for potential targeted next generation sequencing that includes *HER2* and other lung cancer relevant driver mutations, such as EGFR, KRAS, ALK, ROS1, RET and BRAF. Clinical impact of other coexistent molecular alterations (if they are identified) would be analysed in exploratory analyses.

For the purpose of the patient enrolment into the trial, local testing is sufficient.

8.3. *Enrolment*

Verify eligibility, and then enrol the patient by entering the relevant information into the RDE facility ETOPdata according to the information in the ETOPdata User Manual. The date the Informed Consent was signed by the patient and the date signed by the investigator are both required to complete the eligibility checklist.

8.4. *Start of afatinib*

Afatinib treatment should start within 7 days after enrolment of the patient.

9. *Investigational product*

Afatinib is the Investigational Product (IP) used in this trial. Boehringer Ingelheim will provide the IP at no cost for the entire duration of this trial.

The ***Drug Supply Manual*** will describe detailed drug supply logistics as well as labelling, packaging, handling, drug accountability and destruction of unused drugs.

9.1. *Summary of the safety profile*

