14.2. Progression-free survival

This is defined as the time from the date of enrolment until documented progression or death, if progression is not documented. Censoring will occur at the last tumour assessment only if patient is lost to follow-up.

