15.5. Imaging

The following imaging will be done on weeks 6 and 12 from day of first dose of trial treatment, and then every 8 weeks (weeks 20, 28, 36 etc) until progression:

- 15.5.1. CT thorax and upper abdomen

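### SAP Tables 10 and 16 read 12-week PFS from enrolment, so progression found at the week-12 CT, which is timed from first dose, can count as progression-free

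*SAP*

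**What the plan says.** **PFS clock.** Protocol 14.2 starts PFS at enrolment: "This is defined as the time from the date of enrolment until documented progression or death". SAP section 8, Table 10 does the same: "time from the date of enrolment until documented progression or death without documented progression". SAP section 4 words the origin as the earlier of enrolment and treatment start, which is enrolment whenever dosing follows enrolment.

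**Statistic.** Table 10 reports "n(%) of PFS events, 12-week PFS (%) (95% CI), median PFS (in weeks". Table 16 asks for "12-week PFS (%) (95% CI), median PFS (in weekw" by ERBB2 mutation, gender and smoking status.

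**Scan clock.** Protocol 15.5 states: "The following imaging will be done on weeks 6 and 12 from day of first dose of trial treatment". Note 7 of the trial schedule (protocol section 2) agrees: "6 and 12 weeks after first dose of trial treatment and then every 8 weeks (weeks 20, 28, 36 etc) until progression".

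**Gap between the clocks.** Protocol 8.4 states: "Afatinib treatment should start within 7 days after enrolment of the patient".

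**Comparator.** SAP Table 8 takes disease control from the "12-week evaluation (tumor assessment"), that is, from the scan itself and not from a fixed day count.

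Neither document gives a window for the CTs, a rule assigning the week-12 CT to the 12-week PFS time point, or a later read-out time.

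**The concern.** The 12-week PFS is meant to show who was free of progression at week 12, and the week-12 CT is the examination that shows it. With the curve cut at 84 days from enrolment and the scan placed 84 days from first dose, the cut usually comes just before the scan. A progression found at that scan is a failure in Table 8 but a patient still progression-free in Table 10.

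For an on-schedule scan the error runs one way only: the lag from enrolment to dosing can only push detection later, so the PFS rate is either right or too high. The two 12-week figures would stand side by side for the same 13 patients, and the PFS figure could look better for no clinical reason. In Table 16 the subgroup rates would also depend on how quickly each subgroup happened to start treatment.

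What is at stake is a descriptive secondary summary and its exploratory subgroup version.

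**Working it through.** **1. The plan's own figure.** SAP 1.2 reports 6 of 13 patients not free of progression at week 12: 6/13 = 46.2%, which agrees. The complement is 7/13 = 53.8%.

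**2. Where the week-12 CT falls.** Let L be the lag in days from enrolment to first dose, 0 to 7 (protocol 8.4). Taking PFS time as the difference between dates, a progression first found at an on-schedule week-12 CT has time T = 84 + L. The Kaplan-Meier estimate at 12 weeks counts events with T ≤ 84.

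| L (days) | T (days) | T (weeks) | Event by week 12? |
|---|---|---|---|
| 0 | 84 | 12.0 | yes |
| 1 | 85 | 12.1 | no |
| 3 | 87 | 12.4 | no |
| 7 | 91 | 13.0 | no |

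A CT done at least L days early escapes the problem. A CT done late creates it even at L = 0.

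**3. Effect on the reported rate.** Let k be the number of the 6 failures first found at a scan after day 84. With no earlier censoring, 12-week PFS = (7 + k)/13:

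| k | 12-week PFS |
|---|---|
| 0 | 7/13 = 53.8% |
| 1 | 8/13 = 61.5% |
| 2 | 9/13 = 69.2% |
| 3 | 10/13 = 76.9% |

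Each affected patient adds 1/13 = 7.7 points. A Kaplan-Meier run on an assumed split (3 progressions at the week-6 CT, 3 at the week-12 CT, 7 later) gives 76.9% on the enrolment clock for L = 1, 3 or 7, and 53.8% for L = 0 or on the first-dose clock.

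The 95% limits are S^exp(±1.96·se), with se = √[(1−S)/(13·S)] / |ln S|.
- S = 7/13: se = √0.0659/0.619 = 0.415, limits 24.8% to 76.0%.
- S = 9/13: se = √0.0342/0.368 = 0.503, limits 37.3% to 87.2%.

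**4. Plausible size, under assumptions.** The documents give no lags, progression dates or hazard shape. If progression is found only at on-schedule scans, the expected overstatement is P(L ≥ 1) × (S₆ − S₁₂), where S₆ and S₁₂ are the true rates at 6 and 12 weeks from dose.

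- Constant hazard, S₁₂ = 7/13: S₆ = √(7/13) = 0.734, difference 0.195. Every lag at least 1 day gives 19.5 points. Lag uniform on 0–7 days gives 7/8 × 19.5 = 17.1. Lag uniform on 0–3 days gives 3/4 × 19.5 = 14.7.
- Constant hazard, true rate 50%, every lag at least 1 day: √0.5 − 0.5 = 20.7 points.
- 80% of failures by week 6, lag 0–7 days: 0.20 × 6/13 × 7/8 = 8.1 points.

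Simulation (1,000,000 patients per scenario) covers the less tidy cases with S₁₂ = 7/13. With constant hazard it gives:
- 14.2 points with scans ±7 days off schedule
- 9.3 if half of events are dated between scans
- 7.8 with both
- 5.3 if half start on day 0 and half of events are dated between scans

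With 80% of failures by week 6 and half of events dated between scans, it gives 4.4.

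**5. Check of a later read-out.** Reading the enrolment-clock curve at day 98, against a rate of 53.8% at the week-12 scan, gives:
- 53.8–53.9% when progression is found only at scans, with or without the ±7-day variation
- 51.6–51.9% when half of events are dated between scans

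**The case against.** The strongest reply is that size and importance are uncertain.

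- **The starting point is an inference.** SAP 1.2 names no time origin for its 6/13. Had it been counted at 84 days from enrolment, the Kaplan-Meier figure would already be 7/13. But SAP 1.2 says the count was made once all patients had reached the 12-week assessment and sets it beside the stopping rule, so the scan-based reading is the natural one. The mismatch between clocks does not depend on it.
- **k is unknown and may be zero.** This stands. It is zero if every failure was found at week 6, at an early off-schedule CT, or by death before day 84. The real shift comes in steps of 7.7 points, so the expected values show a plausible range and do not predict the result in these 13 patients.
- **Interval method.** SAP 3.1 names the complementary log-log transformation only for medians, so using it for the rate is an assumption. The intervals for k = 0 and k = 2 overlap widely, but a bias of known direction is not excused by imprecision.
- **Day count.** The SAP states no convention. If time were date difference plus one, the problem would arise even at L = 0.
- **The definitions are disclosed and DCR is reported directly.** True. SAP Figure 6 also plots each patient's PFS by primary endpoint, so a failure with a bar beyond 12 weeks would be visible. That would expose the conflict without correcting the rates in Tables 10 and 16.
- **Limited reach.** This stands. Accrual is closed, and median PFS and the log-rank tests do not use the 12-week cut.

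**Conclusion.** The concern holds. Followed as written, the SAP counts a progression first found at an on-schedule week-12 CT as progression-free at 12 weeks whenever dosing began at least 1 day after enrolment (PFS time taken as the date difference). The overstatement is 7.7 points per affected patient, for a number of patients the documents do not give and which may be zero. Under the stated assumptions the expected overstatement is about 5 to 21 points with constant hazard (19.5 at most if the true rate is 7/13), and about 4 to 8 points if 80% of failures occur by week 6. The clock mismatch is certain; these ranges are only as good as their assumptions. The primary DCR, the stopping decision and the error rates are not affected. The read-out should still be corrected before the final analysis.

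**What to change.** In SAP Tables 10 and 16, keep enrolment as the origin, as protocol 14.2 requires. Moving the origin to first dose would leave enrolled patients who never start treatment without one. Read the curve at a landmark that covers the week-12 scan: 12 weeks, plus the 7-day start window, plus a stated scan window. With a 7-day scan window this is 84 + 7 + 7 = 98 days, or 14 weeks, well before the next scheduled CT at week 20. State the scan window and the day-count convention, and label the rate *progression-free through the week-12 assessment*. Assigning progression found at the week-12 CT to week 12 would also remove the conflict, but one rule has to be written down.

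The cost is one line in each of two tables and no new data. The rate becomes the same or less favourable. The later landmark also counts deaths and off-schedule progressions in the added 1 to 2 weeks: about 2 points if half of events are dated between scans, and none if all are found at scans.
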